5.14.1.3 Cabozantinib Discontinuation Criteria

Permanently discontinue cabozantinib for patients with any of the following:

- Any requirement for more than 2 cabozantinib dose reductions (i.e., reduction to less than 20 mg)
- Acute myocardial infarction or new CVA event (including TIA) confirmed by imaging (DWI MRI preferred; refer to [Appendix 6](#))
- Any other Grade ≥ 2 drug-related arterial or venous thromboembolic events including cerebrovascular ischemia, cardiac ischemia, or peripheral or visceral arterial ischemia
- LVEF reduction $\geq 50\%$ from baseline
- Any Grade ≥ 3 hemorrhage
- Grade 4 hypertension or persistent Grade 3 hypertension despite optimal medical management and cabozantinib dose reduction
- Reversible posterior leukoencephalopathy syndrome
- Development of GI perforation or drug-related fistula
- Nephrotic syndrome or recurrent nephrotic range proteinuria (i.e., recurrent 24-hour urine protein ≥ 3 g after dose reduction)
- Any drug-related LFT abnormality that meets the following criteria requires discontinuation:
 - Treatment-emergent ALT or AST > 3 times ULN ($> 2 \times$ baseline AND $> 3 \times$ ULN for patients with baseline elevation)
 - Total bilirubin > 2 times ULN ($> 2 \times$ baseline AND $> 2 \times$ ULN for patients with baseline elevation) or clinical jaundice, without initial findings of cholestasis (e.g., elevated serum alkaline phosphatase) (see Section [8.10](#))
- Any Grade 4 drug-related adverse event or laboratory abnormality, with the following exceptions:
 - Grade 4 neutropenia ≤ 7 days
 - Grade 4 lymphopenia or leukopenia
 - Grade 4 amylase or lipase abnormalities that are not associated with symptoms or clinical manifestations of pancreatitis
 - Isolated Grade 4 electrolyte abnormalities that are not associated with clinical sequelae and are corrected with supplementation/appropriate management within 72 hours of their onset
- Any dosing delay lasting > 8 weeks unless the Medical Monitor is consulted and agrees with the rationale for resuming therapy after a delay > 8 weeks. Note that tumor assessments should continue as per protocol even if dosing is delayed.

- Any adverse event, laboratory abnormality, or intercurrent illness which, in the judgment of the Investigator, presents a substantial clinical risk to the patient with continued cabozantinib dosing.

5.15 Prior and Concomitant Medications

Complications, including fatal events, have occurred in patients who received allogeneic hematopoietic stem cell transplantation before or after nivolumab.

Recording of prior medications should include prior cancer treatments: previous immunotherapy, chemotherapy, targeted therapy, radiation, over-the-counter (OTC) medications, herbs, and dietary supplements.

All medications (prescription and OTC), vitamin and mineral supplements, and/or herbs taken by the patient from 30 days prior to randomization through the last Safety Follow-Up Visit will be documented and recorded, including start and stop date, dose and route of administration, frequency, and indication. Medications taken for a procedure (e.g., biopsy) should also be included.

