EQ-5D-3L	X		X	X	X	Patients should complete the assessment at the start of the clinic visit, prior to dosing and scheduled activities.
FKSI-19	X		X	X	X	
PRO-CTCAE	X		X	X	X	Completed on Days 1 and 22 of every cycle through Cycle 4, and then on Day 1 of the following cycles. See Section 7.6 for further details.

Abbreviations used in this table appear on the final page of [Table 4](#).

Table 3: On-Treatment Schedule of Events for Arm B (Contd)

Procedure ^a	Arm B Cabozantinib 60 mg PO once daily (continuously) OR Sunitinib 50 mg PO once daily (4 weeks on treatment, followed by 2 weeks off treatment) Cycle = 6 Weeks					Notes
	Cycle 1			Cycle 2 and subsequent on-treatment visits		
	Day 1	Day 8 (-1 day)	Day 22 (± 3 days)	Day 1 (± 3 days)	Day 22 (± 3 days)	
Health Care Resource Utilization	X		X	X	X	Site staff will collect the health care resource utilization data at each visit using the CRF.

a. Assessments and visits that occur outside of protocol-specified windows (e.g., for holidays, travel issues, insurance issues) may be acceptable on a case-by-case basis after review by the Medical Monitor.

Abbreviations used in this table appear on the final page of [Table 4](#).

Table 4: Long-Term Follow-Up Schedule of Events

Procedure ^a	Safety Follow-Up Visit 1 ^b	Safety Follow-Up Visit 2 ^b	Survival Follow-Up ^c Every 12 Weeks (± 14 days)	Notes ^d
Safety Assessments				
Vital Signs	X	X		Blood pressure, heart rate, temperature Weight
AE and SAE Assessments	X	X	X	All AEs will be documented until 100 days after the last dose of all study drug(s). SAEs to be collected after the 100-day safety visit if the SAE is deemed to be related or residual toxicities are persisting. Patients will be followed for drug-related toxicities until these toxicities resolve, return to baseline, or are deemed irreversible.
Karnofsky Performance Status	X	X		See Appendix 2 .
Review of Subsequent Medications and Anticancer Therapy	X	X	X	In Survival Follow-up, subsequent anticancer treatment only. Additional subsequent anticancer therapy details such as regimen, setting of the regimen, line of therapy, start date and end date of each regimen, best response to the regimen, and date of progression to subsequent anticancer therapies will be collected.
Laboratory Tests				
Pregnancy Test (WOCBP only)	X	X		Patients (WOCBP) will continue to follow instructions for methods of contraception through 5 months post treatment completion.

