5.6.1 Safety Follow Up

- Safety Follow-up Visit 1 should occur 30 (± 7) days from the last dose of all study drug, or at the time of permanent treatment discontinuation if discontinuation is after the Safety Follow Up Visit 1 window.
- Safety Follow-up Visit 2 occurs 100 (± 7) days from the last dose of all study drug. Safety follow-up visits should occur regardless of initiation of subsequent anticancer therapy.
- Both Safety Follow-Up Visits should be conducted in person.
- Per clinical judgment, the patient may come in earlier for additional follow up.

- Patients will also be followed for safety until resolution or permanent sequelae of all toxicities attributable to study drugs (NKTR-214 and/or nivolumab or TKI) as outlined in Sections 8.5 and 8.8.
- For AE and SAE reporting periods, please refer to Sections 8.5 and 8.7.

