5.6.2 Survival Follow Up

- All patients will be contacted for survival every 12 weeks (\pm 14 days) following the Safety Follow-Up Visit 2 (or following last contact with the patient if Safety Follow-Up Visit 2 is missed).
- Survival visits may be conducted in person or by telephone.
- Information about subsequent anticancer therapy will also be collected during these contacts.
- The Sponsor may request that survival data be collected on all treated patients outside of the scheduled contacts. At the time of this request, each patient will be contacted to determine their survival status unless the patient has withdrawn consent for all contact or is lost to follow-up. Patients are not considered lost to follow up until after demonstration of due diligence with follow-up efforts. Alternative methods to determine survival status may be used (e.g., access to medical records and public record searches) as allowed by local regulations and/or guidelines.
- For patients who discontinue study treatment, radiographic tumor assessments will continue to be collected every 9 weeks (\pm 7 days) from randomization through (and inclusive of) Week 54 and then every 12 weeks (\pm 7 days) until both BICR and Investigator's assessments of tumor images have determined progression, patient withdraws consent, death, initiation of subsequent anticancer therapy, loss to follow up, or study termination by the Sponsor.
- Additional subsequent anticancer therapy details such as regimen, setting of the regimen, line of therapy, start date and end date of each regimen, best response to the regimen, and date of progression after next line of therapy will be collected.
- Survival follow up should continue until patient withdrawal of consent for survival follow up, death, loss to follow-up, or study termination by the Sponsor.

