 - If only the day is missing, the earlier of the following will be used as the stop date:
 - the last day of the month for stop of AE
 - the later of (last known alive date, AE start date if imputed)
 - If the month and day are missing, the earlier of the following will be used as the stop date:
 - December 31st of the year for stop of AE
 - the later of (last known alive date, AE start date if imputed)
- For the determination of prior medication, any medication with a start date prior to C1D1 will be classified as prior medication regardless of the the stop date. Missing or partial dates will be handled as follows:

- If missing day and/or month of the start date, the medication will be classified as prior unless the month and/or year of the start date is after C1D1
- For determination of concomitant medication, the following will be classified as concomitant medication:
 - Any medication with a start date prior to or on C1D1 and continued after C1D1 (this will be considered as both prior and concomitant medication)
 - Any medication with a start date after C1D1, but prior to the last dose date + 100 days or (date of initiation of subsequent anti-cancer therapy – 1 day), whichever is earlier
- Missing or partial dates for concomitant medication will be handled as follows:
 - If missing the day and/or month of the start date, the medication will not be considered as concomitant if the month and/or year of the start date is after the last dose date + 100 days or (date of initiation of subsequent anti-cancer therapy – 1 day), whichever is earlier
 - If missing the day and/or month of the stop date, the medication will not be considered as concomitant if the month and/or year of the stop date is prior to C1D1
 - A medication with completely missing start and stop dates will be classified as concomitant
- In order to calculate duration of immune modulating medication for management of drug-related select AEs or IMAEs (as defined in Section 8.2.2), missing or partial dates for these medications will be handled as follows:

Missing or partial start date:

- If the start date is completely missing, it will not be imputed. Only the number of days that the medication was taken on or after the AE start date will be counted toward the duration of IMM for management of certain AE.
- If only the year is provided, impute the start date to January 1st of the year,
- If only the day is missing, impute the start date to the first day of the month.

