Missing or partial stop date:

- If the stop date is completely missing, impute stop date to the later of (last known alive date, AE start date if imputed)
- If only the day is missing, the earlier of the following will be used as the stop date:
 - the last day of the month for stop of AE
 - the later of (last known alive date, AE start date if imputed)
- If month and day are missing, the earlier of the following will be used as the stop date:

- December 31st of the year for stop of AE
- the later of (last known alive date, AE start date if imputed)
- For death date, the following conventions will be used:
 - If the death date is completely missing but reason for death is present, it will be imputed as the last known alive date
 - If the the death date is partially missing (missing day only, or missing both day and month), the death date and corresponding last known alive date will be imputed in 2 steps:
 1. Imputed as the 1st of the month (missing day only) or January 1st of the year (missing both day and month)
 2. The imputed death date from the 1st step will be compared to the latest alive date captured from multiple sources (unimputed last known alive date), and the maximum of the two will be considered as the imputed death date and last known alive date

Some laboratory analytes may be reported by range (e.g., gamma-glutamyl transferase [GGT] < 17 U/L) and will be imputed by the corresponding boundary (e.g., 17 U/L).

Handling of missing data for efficacy analyses and HRQoL analyses are described in Section 7.5 and Section 7.6, respectively.

No imputation of other missing data is planned.

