For patients off treatment, the treatment-emergent period is defined as the period of time on or after the day (and time, if collected and not missing) of the first dose of study treatment, until: the date of (initiation of new anticancer therapy – 1 day) or (30 days after the date of the last dose of any study treatment), whichever is earlier.

The extended treatment-emergent period will be defined as the period of time on or after the day (and time, if collected and not missing) of the first dose of study treatment until earlier date of (initiation of new anticancer therapy – 1 day) and (100 days after the date of the last dose of any study treatment).

- **Treatment-Emergent Adverse Event (TEAE):**

TEAEs are AEs with an onset date (and time, if collected and not missing) within the treatment-emergent period, or extended treatment-emergent period depending on the analysis

Incomplete start and end dates for TEAEs will be imputed. Any AE will be considered as a TEAE if its status cannot be fully determined because of incomplete data.

- **Last Known Alive Date:** Last known alive date will be defined as the latest alive date on or before data cutoff date, captured from multiple sources. Note that if there is an event date (either an assessment or death) beyond the data cutoff date, the last known alive date will be the data cutoff date. If a patient died before or on the data cutoff date, the last known alive date will be set as the death date. The last known alive date will not be imputed, except in the case that the death date is partially missing (see details in Section 6.4)

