7.4.2 Immune Modulating Medication

The list of anatomic class, therapeutic class and generic name used for the selection of immune-modulating medication (IMM) will be provided at the time of the database lock.

The percentage of patients who received immune-modulating concomitant medications for

- Management of drug-related select adverse events (any Grade, Grade 3-5) by select AE category/subcategory (see Section 8.2 for select AEs)
- Management of IMAEs (any grade, grade 3-5) by IMAE category (see Section 8.2.2 for IMAEs) will be reported by medication class and generic term.

For each category/subcategory of drug-related select AEs (any grade, grade 3-5) and IMAEs (any grade, grade 3-5), the following will be reported:

- Total duration of IMM use (excluding overlaps), duration of high dose of corticosteroid, initial dose of corticosteroid, and tapering duration (summary statistics)

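### An immune-modulating drug with no stop date is counted as used up to the last known alive date, although routine medication recording ends at the last Safety Follow-Up Visit

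*Protocol*

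**What the plan says.** **What is recorded, and until when.** Protocol 5.15 states that all medications "taken by the patient from 30 days prior to randomization through the last Safety Follow-Up Visit will be documented and recorded", with start and stop dates. Protocol 5.6.1 places that visit: "Safety Follow-up Visit 2 occurs 100" (± 7) days from the last dose of all study drug. After it, Protocol 5.6.2 says "All patients will be contacted for survival every 12 weeks". In the long-term follow-up table (Protocol 1.2, Table 4), the row on medications and anticancer therapy notes: "In Survival Follow-up, subsequent anticancer treatment only".

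**How a missing stop date is filled.** SAP 6.4 gives a rule specific to IMM, introduced by "In order to calculate duration of immune modulating medication for management of drug-related select AEs or IMAEs". For stop dates it says: "If the stop date is completely missing, impute stop date to the later of (last known alive date, AE start date if imputed"). Partial dates are bounded by month or year end; completely missing dates are not.

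**What the last known alive date is.** SAP 6.6: "Last known alive date will be defined as the latest alive date on or before data cutoff date, captured from multiple sources". If the patient has died, it is the death date.

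**What is reported.** SAP 7.4.2 lists, for each category of drug-related select AE and IMAE, "Total duration of IMM use (excluding overlaps), duration of high dose of corticosteroid, initial dose of corticosteroid, and tapering duration (summary statistics"). No censoring is mentioned.

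**The concern.** The two documents use different clocks. Non-anticancer medication is routinely recorded up to about 100 days after the last dose. The last known alive date keeps moving with each survival contact, up to the data cutoff or death. An IMM still in use at the last Safety Follow-Up Visit would typically have no stop date, and SAP 6.4 has no separate rule for ongoing use. The completely-missing rule then appears to apply, and survival follow-up is added to the time on drug as if the course had been seen to end.

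At stake is the description of how immune-related toxicity was managed: total IMM duration and any high-dose or taper duration whose final record is open. SAP 8.2.1 and 8.2.2 label the select AE and IMAE analyses as support for the EU and US submissions. A duration that lengthens when only the cutoff has moved misdescribes that management.

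**Working it through.** The plan states no figure for this point, so there is none to reproduce. The check compares the texts and then illustrates the size.

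**1. Is there a cap anywhere?** Not for IMM duration. The 100-day limit in SAP 7.4.1 governs when a concomitant medication starts, not when it ends. The SAP treats comparable quantities differently:

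| Quantity | SAP section | Handling when the end is not seen |
|---|---|---|
| Completely missing AE stop date | 6.4 | No imputation |
| Resource-use person-time | 7.7 | Ends at the earlier of last dose + 100 days and last known alive date |
| AE time-to-resolution | 8.2.1.3, 15.4.2 | Censored at last known alive date, Kaplan-Meier |
| IMM duration | 6.4, 7.4.2 | Last known alive date counted as the stop date, plain summary statistics |

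**2. One patient (dates assumed).** Last dose day 90, steroid start day 95, last Safety Follow-Up Visit day 190, last known alive day 600, no stop date.
- SAP rule: 600 − 95 + 1 = 506 days.
- Up to the last safety visit: 190 − 95 + 1 = 96 days.
- Difference: 410 days.

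**3. Average over patients followed beyond the visit.**

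Inputs from the documents:
- Accrual of 600 at 28 per month: 600/28 = 21.43 months (SAP 6.2.1).
- Exponential OS, TKI median 26 months, HR 0.63 (SAP 6.2.2, intermediate- or poor-risk), so the Arm A median is 26/0.63 = 41.3 months. Hazards: λ = ln 2/41.27 = 0.01680 per month (A) and ln 2/26 = 0.02666 (B).
- Visit delay: 100/30.4375 = 3.29 months.
- Outer cutoff of 36 months, from the end-of-study definition in Protocol 5.7.

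Assumptions: uniform entry; steroid start at month 5; last dose at month 6; steroid still open at the visit (month 9.29); patients known alive up to the cutoff. With 12-week contacts the real date can lag by up to about 2.8 months.

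Medication data cover 9.29 − 5 = 4.29 months.

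For a cutoff x months after last entry, time available after the visit is uniform on (a, b), with a = max(0, x − 9.29) and b = x + 21.43 − 9.29. Because OS is exponential, the mean excess is

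(1/λ) × {1 − [exp(−λa) − exp(−λb)] / [λ(b − a)]}.

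| Cutoff x | a, b | Excess A | Imputed mean A (+4.29) | Excess B | Imputed mean B |
|---|---|---|---|---|---|
| 6 | 0, 18.14 | 8.22 | 12.5 | 7.77 | 12.1 |
| 18 | 8.71, 30.14 | 16.35 | 20.6 | 14.86 | 19.1 |
| 36 | 26.71, 48.14 | 27.61 | 31.9 | 23.49 | 27.8 |

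The ratio to 4.29 months in Arm A is 2.9, 4.8 and 7.4.

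**4. Sensitivity to last dose (Arm A, steroid start one month earlier).** For last dose at month 3, 6 or 12, the imputed mean is 13.7, 12.5 or 10.0 months at the first cutoff and 33.5, 31.9 or 28.5 at the last. For last dose at month 24 the median excess is about 0.1 months at the first cutoff, because almost no patient has passed the visit by then.

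**5. Effect on a group mean.** The rise equals the share of affected records times the mean excess. In Arm A the excess is about 250 days at the first cutoff (8.22 × 30.4375) and 498 days at 18 months. The documents give no share. Assumed shares of 2%, 5%, 10% and 20% give rises of 5, 12.5, 25 and 50 days at the first cutoff, and 10, 25, 50 and 100 days at 18 months.

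**The case against.** **Medication after the visit is not wholly unseen.** Table 4 and Protocol 5.6.1 follow drug-related toxicities until they resolve or are judged permanent. Protocol 8.8 follows unresolved related SAEs past the last safety visit, and Protocol 8.7 has medication used to treat an SAE recorded. This stands: it would be wrong to infer that no such drug can ever receive a stop date. The gap is mainly non-serious events, whose follow-up ends at the last safety visit under Protocol 8.5. The imputation rule is unchanged either way.

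**Ongoing records may be handled separately.** The case report form is not in these documents, so an ongoing field may exist. That limits certainty, but the SAP states no rule for such a field.

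**Some use really continues.** The protocol foresees physiologic corticosteroid replacement for endocrinopathies, and the IMM list is supplied only at database lock. For such use the last known alive date may be nearer the truth than day 100. This stands, and it argues against a hard cap reported as completed duration.

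**The longer-living arm would seem to need longer immunosuppression.** A reader might infer this, but the documents lend it little support. IMAE summaries are for Arm A only (SAP 8.2.2), so only select AEs can be compared. Among affected records the gap is 12.5 against 12.1 months at the first cutoff and 31.9 against 27.8 at the last. With a 10% share, the gap in group means is about 1 day at the first cutoff and about 5 days at 18 months.

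**Not every measure moves.** Initial dose does not depend on the stop date. If dose steps are entered as separate records, only the last stays open and high-dose duration changes little. With few affected records, the median barely moves.

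**Conclusion.** The point holds as a defect in one imputation rule for a descriptive safety summary. Where an IMM record has no stop date and the patient is followed past the last Safety Follow-Up Visit, the SAP reports follow-up time without routine medication recording as completed use, and the figure rises with the cutoff.

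Among such records the inflation is large: a mean excess of about 8 months at the first illustrative cutoff and about 28 at the last in Arm A, given the plan's accrual and OS assumptions and an assumed last dose at month 6. Patients on treatment, or within 100 days of last dose at cutoff, are unaffected. How far any reported summary moves cannot be settled from the documents, because the number of open records is unknown.

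A reader might go further and doubt the efficacy results or the safety comparison between arms. Neither follows: no primary or key secondary endpoint uses these dates, and the survival-driven arm difference is small. With one interim and one final efficacy analysis planned, the drift across cutoffs is also limited. This is a minor correction.

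**What to change.** In SAP 6.4, replace the rule for a completely missing IMM stop date. Flag the record as ongoing and censor it at the earliest of death, data cutoff and the last date medication use was documented. That last date is the last Safety Follow-Up Visit, or a later SAE report where one exists.

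In SAP 7.4.2, summarise total IMM duration, and any high-dose or taper duration left open, by Kaplan-Meier with that censoring, as is already planned for AE time-to-resolution, and report the number of patients ongoing. Do not present the censoring date as the end of a completed course.

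The cost is one SAP rule and a small programming change, with no new data. The downside is that durations for ongoing users become stated minimums, and a Kaplan-Meier median may not be reached in small categories.
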